1. SYNOPSIS

Protocol Title: An open-label, randomised, single-dose, two-period cross-over study to evaluate bioequivalence of SK101804 Cefixime 200 mg/5 mL suspension versus Cefixime 200 mg/5 mL suspension reference product in healthy adult participants under fasting conditions.

Short Title: Bioequivalence study between SKF101804 cefixime 200 mg/5 mL suspension versus cefixime 200 mg/5 mL suspension reference product in healthy adult participants under fasting conditions

Rationale:

This study will determine if cefixime 200 mg/5 mL powder for suspension (test formulation: SKF101804; FIXVAL™, GlaxoSmithKline Pakistan Limited) is bioequivalent to cefixime 200 mg/5 mL suspension (reference formulation: Cefspan, manufactured by Barrett Hodgson Pakistan under licence from Astellas Pharma, Japan).

Objectives and Endpoints:

Objective	Endpoint
Primary	
To determine if 200 mg/5 mL cefixime (SKF101804) powder for suspension is bioequivalent to reference 200 mg/5 mL cefixime suspension in healthy adult participants under fasting conditions.	Plasma PK parameters: $AUC_{(0-t)}$ and C_{max} , for cefixime in relevant treatments
Secondary	
To assess secondary PK parameters of 200 mg/5 mL cefixime powder for suspension (SKF101804) relative to reference 200 mg/5 mL cefixime suspension in healthy adult participants under fasting conditions.	Plasma PK parameters: $AUC_{(0-\infty)}$, t_{max} , $\%AUC_{ex}$ and $t_{1/2}$ for cefixime in relevant treatments.
To compare the safety and tolerability of a single dose of 200 mg/5 mL cefixime powder for suspension (SKF101804) with reference 200 mg/5 mL cefixime suspension, in healthy adult participants under fasting conditions.	Adverse events (AE), clinical laboratory values (Haematology and Biochemistry) and vital signs

$AUC_{(0-\infty)}$ = Area under the concentration-time curve from time zero (pre-dose) extrapolated to infinite time; $\%AUC_{ex}$ = Percentage of $AUC_{(0-\infty)}$ obtained by extrapolation; $AUC_{(0-t)}$ = Area under the plasma concentration versus time curve from time zero to t, where t is the time of the last quantifiable concentration; C_{max} = Maximum observed concentration; PK = Pharmacokinetic $t_{1/2}$ = Terminal phase half-life; T_{max} = Time of occurrence of C_{max}

Overall Design:

This is a Phase I, open label, balanced, randomised, single dose, two-way crossover study, enrolling 28 healthy participants at a single centre.

Each enrolled study participant will take part in two treatment periods in accordance with the randomisation schedule. The treatment periods will be separated by a washout period of at least 7 days and no more than 14 days.

Number of Participants:

Up to 28 participants will be randomized to yield at least 24 evaluable participants completing the study.

Treatment Groups and Duration:

Study treatments will be referred to as Test and Reference throughout the protocol:

- Treatment A – Test: SKF101804 (FIXVAL™) 200 mg cefixime (200 mg/5 mL powder for oral suspension).
- Treatment B Reference: (Cefspan), 200 mg cefixime (200 mg/5 mL powder for oral suspension).

Treatment periods 1 and 2 will be separated by a washout period of 7 to 14 days.

The total duration in the study for each participant is expected to be 5 to 7 weeks, from screening to their last visit.

Treatment Groups and Sequences:

- Participants will be randomised to one of two sequences (A-B or B-A), and administered a single oral dose of one of the two treatments (A or B) in each treatment period, such that each participant receives a dose of each treatment in the study.

2. SCHEDULE OF ACTIVITIES (SOA)

Details of study assessments and collection windows are given in the Schedule of Activities (SoA), [Table 1](#).

Table 1 Schedule of Activities

Procedure	Screening (Day -21 to Day -1)	Treatment Periods 1 and 2			Follow-up (within 7 days post last dose or at discontinuation)	Notes
		Day -1	Day 1	Day 2		
Informed consent	X					
Inclusion and exclusion criteria	X	X				Refer to Section 6 . Recheck clinical status before randomization.
Domiciled to the Unit		X	X	X		Participants to be admitted on Day -1 of each treatment period, and discharged on Day 2.
Outpatient Visits	X					
Discharge				X		
Participants will be discharged from the unit after the collection of the 24 hours post dose PK sample, vital signs, lab assessments and, urinalysis; following review by a doctor to assess participant safety.
 
At the end of treatment period 2, in addition to the other assessments taken at 24 hours post dose (Day 2), all female participants will also have a urine pregnancy test, prior to discharge.
 
Participants who have normal safety assessment results at the end of treatment period 2 do not require a follow up.

Procedure	Screening (Day -21 to Day -1)	Treatment Periods 1 and 2			Follow-up (within 7 days post last dose or at discontinuation)	Notes
		Day -1	Day 1	Day 2		
Follow up (Phone Call or Outpatient Visit)					X	If a participant's safety assessments (medical exam, vital signs, ECG, Lab assessments) are abnormal and clinically significant at Treatment Period 2 discharge or if a participant has an open AE, then a follow up phone call or outpatient clinic visit is required within 7 days (+2 days if required). Enquiries on the participant's general health, including any AEs/SAEs/concomitant medication must be recorded in the medical notes.
Demography and Medical history (includes substance usage)	X					Substances: Drugs, Alcohol, tobacco and caffeine
Physical examination	X	X				Screening: Full physical examination including height and weight Day -1: Abbreviated physical exam (excluding height and weight)
Past and current medical conditions	X	X				
Pregnancy test (WOCBP only)	X	X		X		Serum β -hCG: at screening. Urine β -hCG: at Day-1 of both Treatment periods and at the end of Treatment period 2 on Day 2.
HIV, Hepatitis B and C screening	X					Testing for Hepatitis B (HBsAg) and Hepatitis C (HepC antibody) at screening is not required if this was performed within 3 months prior to first dose of study treatment. Participants, who are positive for Hepatitis C antibody due to prior resolved disease, must have a confirmatory negative Hepatitis C RNA test.

Procedure	Screening (Day -21 to Day -1)	Treatment Periods 1 and 2			Follow-up (within 7 days post last dose or at discontinuation)	Notes
		Day -1	Day 1	Day 2		
Laboratory assessments (include liver chemistries) ^a	X	X		X		
Screening: Participants are required to fast at least 10 hours prior to the Screening Laboratory assessment. Haematology, Biochemistry, Coagulation profile (PT and aPTT) and Urinalysis are assessed.
 
Day -1: Haematology, Biochemistry and Urinalysis are assessed.
 
Day 2: Haematology, Biochemistry and Urinalysis samples are obtained 24 hours post dose, prior to discharge. Additional safety labs must be collected as deemed necessary at the Investigator's discretion.

Urine Drug/Urine Cotinine/Breath alcohol	X	X				
12-lead ECG ^a	X					12-lead ECG will be completed at screening only.
Vital signs ^a	X		X	X		
Vitals will be taken at:
 
 • Screening, • Day 1: pre-dose and post dose at, 2.00, 4.00, and 6.00 hours • Day 2: 24.00 hours post-dose. 
Post dose vitals to be taken \pm30min of each time point.

Randomization			X			Day 1 of treatment period 1 only.

Procedure	Screening (Day -21 to Day -1)	Treatment Periods 1 and 2			Follow-up (within 7 days post last dose or at discontinuation)	Notes
		Day -1	Day 1	Day 2		
Study treatment			X			Screening and Day -1 results must be reviewed by physician prior to randomisation and dosing. Participants to be fasted 10.00 hours prior and 4.00 hours post dose. Dosing between Treatment periods will be separated by a washout of 7 -14 days. Participants will remain in a sitting or semi-supine position for at least 20 minutes after dosing on Day 1 of each treatment period.
AE Review		←-----→				Collected from the start of dosing (Day 1, Treatment period 1) to the participant's final discharge from study at the end of Treatment Period 2, follow up call or last outpatient visit, whichever is the latest.
SAE review	←-----→					Any SAEs assessed as related to study participation (e.g. investigational product, protocol-mandated procedures, invasive tests) or related to a GSK concomitant medication will be recorded from the time a participant consents to participate in the study up to and including any follow up contact.
Concomitant medication review	←-----→					

Procedure	Screening (Day -21 to Day -1)	Treatment Periods 1 and 2			Follow-up (within 7 days post last dose or at discontinuation)	Notes
		Day -1	Day 1	Day 2		
Pharmacokinetics ^a			X	X		
Day 1: Pre-dose, 0.5, 1.0, 1.5, 2.0, 2.5, 3.0, 3.5, 4.0, 4.5, 5.0, 6.0, 7.0 8.0, 10.0, 12.0, 16.0 and 20.0 hours post dose Day 2: 24.00 hours post dose
 
Pre-dose sample will be taken within 60 minutes before dose. Post dose samples for:
 
 • 0.50 -2.00 hours will be taken \pm2 min; • 2.50 – 10.00 hours will be taken \pm5 min; and • 12.00 – 24.00 hours will be taken \pm10 min.

a. The order of assessments to be followed where an ECG, Vital Signs and Blood sample for either PK or Lab assessments are required at the same time point, should always be first ECG, second vital signs and lastly blood sampling, whilst ensuring that the timing for PK blood samples remains within the sampling window.

Note: PK= pharmacokinetic; ECG= electrocardiogram; AE= adverse events; SAE= serious adverse events; WOCBP= woman of childbearing potential; HBsAg= Hepatitis B surface antigen ; RNA= ribonucleic acid; PT= prothrombin time; aPTT= activated partial thromboplastin time; GSK= GlaxoSmithKline

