4. OBJECTIVES AND ENDPOINTS

Objectives	Endpoints

Primary
 
To determine if 200 mg/5 mL cefixime (SKF101804) powder for suspension is bioequivalent to reference 200 mg/5 mL cefixime suspension in healthy adult participants under fasting conditions.
	
Plasma PK parameters: $AUC_{(0-t)}$ and C_{max}, for cefixime in relevant treatments

Secondary
 
To assess secondary PK parameters of 200 mg/5 mL cefixime powder for suspension (SKF101804) relative to reference 200 mg/5 mL cefixime suspension in healthy adult participants under fasting conditions.
 
To compare the safety and tolerability of a single dose of 200 mg/5 mL cefixime powder for suspension (SKF101804) with reference 200 mg/5 mL cefixime suspension, in healthy adult participants under fasting conditions.
	
Plasma PK parameters: $AUC(0-\infty)$, t_{max}, $\%AUC_{ex}$ and $t_{1/2}$ for cefixime in relevant treatments.
 
Adverse events (AE), clinical laboratory values (Haematology and Biochemistry and vital signs)

$AUC_{(0-\infty)}$ = Area under the concentration-time curve from time zero (pre-dose) extrapolated to infinite time; $\%AUC_{ex}$ = Percentage of $AUC(0-\infty)$ obtained by extrapolation; $AUC_{(0-t)}$ = Area under the plasma concentration versus time curve from time zero to t, where t is the time of the last quantifiable concentration; C_{max} = Maximum observed concentration; PK = pharmacokinetic $t_{1/2}$ = Terminal phase half-life; T_{max} = Time of occurrence of C_{max}

[figure not shown]

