8.1.3. Temporary Discontinuation

Participants withdrawn from study treatment, will continue in the study until completion of their follow up visit for the study period.

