9.2.1. Time Period and Frequency for Collecting AE and SAE Information

- All SAEs will be collected from the time a participant consents to participate in the study until the follow-up visit at the time points specified in the SoA (Section 2).

- All AEs will be collected from the start of IP administration until the follow-up contact at the time points specified in the SoA (Section 2).
- Medical occurrences that begin before the start of study treatment but after obtaining informed consent will be recorded on the Medical History/Current Medical Conditions section of the case report form (CRF) not the AE section.
- All SAEs will be recorded and reported to the sponsor or designee immediately and under no circumstance should this exceed 24 hours, as indicated in [Appendix 4](#). The investigator will submit any updated SAE data to the sponsor within 24 hours of it being available.
- Investigators are not obligated to actively seek AEs or SAEs in former study participants. However, if the investigator learns of any SAE, including a death, at any time after a participant has been discharged from the study, and he/she considers the event to be reasonably related to the study treatment or study participation, the investigator must promptly notify the sponsor.
- The method of recording, evaluating, and assessing causality of AEs and SAEs and the procedures for completing and transmitting SAE reports are provided in [Appendix 4](#).

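### AEs are collected for about 24 hours after the second dose but through a 7 to 14 day washout after the first, so delayed events after the second dose are not actively sought in participants who are well at discharge

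*Combined protocol and SAP*

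**What the plan says.** In the Schedule of Activities (Section 2, Table 1), the Discharge row sets the same release point in each period: "Participants will be discharged from the unit after the collection of the 24 hours post dose PK sample" and the other Day 2 checks. For the end of the second period it adds: "Participants who have normal safety assessment results at the end of treatment period 2 do not require a follow up". The Follow up row requires a phone call or outpatient visit within 7 days, extendable by 2, only if safety assessments "are abnormal and clinically significant at Treatment Period 2 discharge or if a participant has an open AE". The heading of that column also covers discontinuation, but the trigger in the row does not mention it.

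The AE Review row gives the collection period: "Collected from the start of dosing (Day 1, Treatment period 1) to the participant's final discharge from study" at the end of Period 2, or to a follow-up call or last outpatient visit if that is later.

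Other sections are worded as if a follow-up happens:
- Section 9.2.1: "All AEs will be collected from the start of IP administration until the follow-up contact at the time points specified in the SoA". The same section collects SAEs until the follow-up visit.
- Section 8.1.3: participants withdrawn from treatment "will continue in the study until completion of their follow up visit for the study period".
- Section 7.7: the restriction on other medicines lasts until the follow-up visit is complete.

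Comparing the safety and tolerability of the two products is a secondary objective (Section 4). Section 10.3.5 and Appendix 7 summarise AEs by treatment. Neither defines a post-dose window or says how an event starting in the washout is handled. The only AE timing rules in Appendix 7 are for imputing missing start dates and times.

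**The concern.** The two doses taken by one participant are observed for very different lengths of time. After the first dose, an event starting on day 3 or day 6 can be picked up when the participant returns for Period 2. After the second dose, the same event in someone who was well at 24 hours has no scheduled contact at which it would be asked about.

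The trigger for follow-up is status at discharge. It finds out what became of events already visible at 24 hours, but it cannot find a first onset after that. Section 9.2.1 leaves a passive route only: an SAE that the investigator learns of later and considers reasonably related must be notified. A delayed non-serious AE has no route at all.

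At stake is how well the AE tables serve the secondary safety objective. Pooled by treatment without a common window, they mix doses observed for a day with doses observed for one to two weeks.

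**Working it through.** The plan states no figure for AE observation time, so there is none to reproduce. Its sample size (24 evaluable, 28 entered, Section 10.1) concerns the bioequivalence test and does not depend on follow-up.

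**Inputs.** 28 randomised, 14 per sequence (Section 7.3, Table 2); at least 24 evaluable completers (Section 5.2); doses 7 to 14 days apart (Schedule, Study treatment row); Period 2 discharge at about 24 h; half-life 3 to 4 h (Section 3.2). Section 5.1 counts the washout from Period 1 Day 2. If that runs to Period 2 dosing, the doses are about 8 to 15 days apart.

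**Collection time per dose, 28 completers, no follow-up contacts**

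| | Days per dose | Person-days |
|---|---|---|
| After dose 1 | 7 to 14 | 28 × 7 = 196 to 28 × 14 = 392 |
| After dose 2 | about 1 | 28 × 1 = 28 |

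The ratio is 196/28 = 7 to 392/28 = 14, or 8 to 15 on the Section 5.1 count. It compares the time over which an event would count, not the intensity of observation: participants are at home in the washout, and the next scheduled visit is Period 2 Day -1.

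**Doses affected.** If all complete, 28/56 = 50%. With 24 completers, 24/(28 + 24) = 24/52 = 46%. Both are ceilings, because anyone meeting the trigger is contacted. The documents give no rate for that. If 10%, 25% or 50% met it (assumed), short-window doses would be 28 × 0.90 = 25.2, 28 × 0.75 = 21 or 28 × 0.50 = 14 of 56, that is 45%, 37.5% or 25%.

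**By product.** Each product is given 14 times in Period 1 and 14 times in Period 2. Person-days per product are 14 × 7 + 14 × 1 = 112 to 14 × 14 + 14 × 1 = 210, the same for test and reference. As a stress case, suppose four participants, all from one sequence, drop out at the end of washout (assumed). One product then has 98 + 10 = 108 against 112, or 196 + 10 = 206 against 210, a shortfall of 3.6% or 1.9%. Earlier dropout would widen this.

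**Exposure covered by 24 h.** 24/4 = 6 to 24/3 = 8 half-lives, leaving 0.5^6 = 1.6% to 0.5^8 = 0.4% of the drug. The gap therefore concerns only events that start after exposure has largely ended.

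**Sensitivity.** Let p be the chance per dose of an AE starting after 24 h (assumed, independent between doses, always reported when asked). The chance of recording at least one is 1 − (1 − p)^28 if only first doses are followed, and 1 − (1 − p)^56 if both are.

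| p | First doses only | Both doses |
|---|---|---|
| 1% | 24.5% | 43.0% |
| 5% | 76.2% | 94.3% |
| 10% | 94.8% | 99.7% |

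**The case against.** The strongest reply is that this is a disclosed design choice. Section 9.2.1 defers to the time points in the Schedule, and the AE Review row there states the end point clearly. The SAE row and Section 9.2.5 also treat follow-up as conditional. Cefixime is a marketed drug given once to healthy adults, 24 hours covers 6 to 8 half-lives, and Section 3.3.1 calls most of the listed risks uncommon to very rare. At most 28 extra calls would say little about rare reactions. All of this stands as a reason to rank the point below anything touching the primary analysis. It does not remove the uneven windows or the missing rule in Appendix 7.

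A reader might infer more than the documents support:
- *The safety comparison is biased between products.* It is not, given equal sequences. Section 5.2 also keeps the sequence balance when participants are replaced.
- *Delayed events after half of all doses are missed.* Half is a ceiling. Follow-up is not required, which is different from prohibited, and related SAEs that become known are still reported. The accurate term is not actively sought.
- *A fixed share of AEs is lost.* If a fraction f of onsets within 7 days falls in the first 24 h, and all are captured after dose 1, overall capture is (1 + f)/2. That is 57% for even onset (f = 1/7), but anything from 50% to 100% as f runs from 0 to 1. The documents give no onset distribution.
- *Section 9.4.4 shows that the plan itself regards 24 hours as too short.* Its 7 days govern repeat testing of clinically significant laboratory abnormalities; they do not set an AE surveillance period.
- *Someone withdrawn after Period 1 is never followed.* The column heading, the open-AE limb of the trigger and Section 8.1.3 partly cover this case. The wording is inconsistent rather than silent.

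**Conclusion.** The point holds as a limit on safety capture. For participants with normal assessments and no open AE at Period 2 discharge, AE collection ends about 24 hours after the second dose, against 7 to 14 days after the first. This applies to at most 28 of 56 doses. The effect is lower sensitivity to delayed AEs and AE rates that cannot be compared between periods. Test and reference are affected alike.

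The window lengths and dose counts follow from the documents. The share of participants who would meet the trigger, the timing of AE onset and the rate of delayed AEs are not given, so the number of events lost cannot be stated.

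Separately, the waiver in the Schedule needs reconciling with Sections 7.7, 8.1.3 and 9.2.1. The trigger also has loose ends. It leaves unclassified any result that is abnormal but not clinically significant, and it lists the ECG among the discharge assessments although the ECG is done at screening only.

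The bioequivalence conclusion is untouched. This is a low-cost improvement to a secondary objective.

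**What to change.** 1. In the Schedule of Activities, replace the waiver so that the follow-up phone contact already defined there applies to every dosed participant, including those who discontinue after Period 1. Align the trigger text with the column heading, and Sections 7.7, 8.1.3 and 9.2.1 with the result. Whether anyone needs an outpatient visit instead of a call remains a clinical decision for the sponsor.
2. In Appendix 7, summarise AEs by treatment over the same post-dose window in both periods, and list later washout-onset events separately. The window should be no longer than the shortest dose-to-dose interval, which is 7 days in the Schedule. Because the contact may fall anywhere within its allowed period, it should be timed at or after the end of that window; otherwise the second dose is still observed for less time.

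With a contact at day 7 for 28 completers, collection after the second dose rises from 28 to 28 × 7 = 196 person-days, against 196 to 392 after the first.

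The cost is at most about 28 short calls, some already required, and a few lines of text. The last participant leaves the study about a week later: 7 − 1 = 6 days after discharge, or 9 − 1 = 8 with the extension. Sample size and power do not change.

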3. INTRODUCTION

3.1. Study Rationale

GlaxoSmithKline (GSK) Product, SKF101804 (cefixime) 200 mg/5 mL suspension is marketed in Pakistan as FIXVAL™. This study is required to determine whether the test product SKF101804/FIXVAL™ is bioequivalent to the reference cefixime 200 mg/5mL suspension (Cefspan) in healthy adult participants under fasting conditions.

Bioequivalence (BE) will be declared if the 90% confidence interval (CI) for the true ratio of test to reference geometric means falls entirely within the range of 0.80 to 1.25 for all primary PK parameters.

3.2. Background

Cefixime is an orally active third generation cephalosporin indicated for the treatment of acute exacerbations of chronic bronchitis, acute otitis media, uncomplicated acute cystitis and uncomplicated pyelonephritis, caused by susceptible organisms. Like other cephalosporins, cefixime exerts its antibacterial activity by binding to and inhibiting the action of penicillin-binding proteins involved in the synthesis of bacterial cell walls. This leads to bacterial cell lysis and cell death [[Cefixime Summary of Product Characteristics, 2015](#); [Suprax Product Monograph, 2016](#)].

The pharmacokinetic properties of cefixime show rapid absorption with peak serum concentrations reached within 2-6 hours following oral administration of the tablet or suspension. Cefixime has a half life of 3-4 hours and predominantly excreted in the urine and bile [[Cefixime Summary of Product Characteristics, 2015](#); [Suprax Product Monograph, 2016](#)]. The oral bioavailability of cefixime tablets and suspension is about 40-50% and is unaffected by food; however time to maximal absorption is increased approximately by 0.8 hours when administered with food. The AUC is approximately 26.4% greater and the Cmax approximately 20.7% greater with the oral suspension compared to the tablet. Because of this lack of bioequivalence between tablet/capsule and suspension consideration needs to be given if the oral suspension is to be substituted for the tablet/capsule.

A detailed description of the chemistry, pharmacology, efficacy and safety of cefixime is provided in the cefixime product label [[Cefixime Summary of Product Characteristics, 2015](#); [Suprax Product Monograph, 2016](#)]

